5.2.1. Analyses for Binary Endpoints

For binary endpoints (eg, proportion of participants with SARS-CoV-2 RNA <LLOQ in plasma over time, proportion of participants with COVID-19-related hospitalization >24 hours, or death from any cause through Day 28, etc), proportion of participants with the event will be summarized for each group.

5.2.2. Analyses for Continuous Endpoints

For continuous endpoints, (eg, change from baseline in SARS-CoV-2 RNA level in NP swabs and in plasma over time), results and/or changes from baseline over time, as applicable will be summarized with descriptive statistics (mean, SD, etc).

5.2.3. Analyses for Time-to-Event Endpoints

For time-to-event endpoints (eg, time to first NP swab SARS-CoV-2 RNA<LLOQ [<2.0 log_{10} copies/mL] for participants with NP swab SARS-CoV-2 RNA ≥LLOQ at baseline), Kaplan-Meier analysis where tabular summaries of the Kaplan-Meier curves providing the median and quartiles, will be provided for each treatment group. In addition, the Kaplan-Meier curves will be presented graphically.

5.3. Methods to Manage Missing Data

For SARS-CoV-2 RNA data, samples producing a result of <LLOQ or undetectable will not be considered missing, but rather will be imputed using values of 1.7 [log₁₀(50)] or 0.0 log₁₀ copies/mL, respectively. Missing SARS-CoV-2 RNA data will not be imputed.

As all analyses are descriptive, missing endpoint data will result in a summary where the N for that endpoint (and time point) is smaller than the total N of the corresponding analysis set. No imputation of the missing data will be performed.

For safety data, missing and partial dates will be programmatically handled according to Pfizer standards.

6. ANALYSES AND SUMMARIES

6.1. Primary Endpoint(s)

The primary endpoint, summarized separately for the main study population and the population with rebound, is the proportion of participants with sustained NP swab SARS-CoV-2 RNA <LLOQ (defined as <2.0 log₁₀ copies/mL) from Day 15 through Day 44.

Sustained is defined as NP swab SARS-CoV-2 RNA level not $\geq 2.0 \log_{10}$ copies/mL at any study visit (through Day 44) following the first study visit where the participant's NP swab SARS-CoV-2 RNA <LLOQ.

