**Study Arms and Duration:**

Eligible participants for this study will be randomly assigned (1:1:1) to receive nirmatrelvir plus ritonavir orally q12h as specified in the table below.

Study Intervention(s)				
Intervention Name	Nirmatrelvir	Placebo for nirmatrelvir	Ritonavir	Placebo for ritonavir
Arm Name (group of participants receiving a specific treatment or no treatment)	nirmatrelvir/ritonavir	placebo	nirmatrelvir/ritonavir	placebo
Unit Dose Strength(s)	150 mg	0 mg	100 mg	0 mg
Route of Administration	Oral	Oral	Oral	Oral
Use	Experimental	Placebo	Experimental	Placebo
IMP or NIMP/AxMP	IMP	IMP	IMP	IMP

Study Arm(s)			
Arm Title	Nirmatrelvir/ritonavir 5-day	Nirmatrelvir/ritonavir 10-day	Nirmatrelvir/ritonavir 15-day
Arm Type	Experimental, placebo	Experimental, placebo	Experimental
Arm Description	Participants will receive nirmatrelvir/ritonavir 300 mg/100 mg (or 150 mg/100 mg for participants with eGFR $\geq$ 30 to <60 mL/min/1.73 m  or eCrCl $\geq$ 30 to <60 mL/min) q12h from Day 1 through Day 5 followed by placebo for nirmatrelvir/placebo for ritonavir q12h for Day 6 through Day 15.	Participants will receive nirmatrelvir/ritonavir 300 mg/100 mg (or 150 mg/100 mg for participants with eGFR $\geq$ 30 to <60 mL/min/1.73 m  or eCrCl $\geq$ 30 to <60 mL/min) q12h from Day 1 through Day 10 followed by placebo for nirmatrelvir/placebo for ritonavir q12h for Day 11 through Day 15.	Participants will receive nirmatrelvir/ritonavir 300 mg/100 mg (or 150 mg/100 mg for participants with eGFR $\geq$ 30 to <60 mL/min/1.73 m  or eCrCl $\geq$ 30 to <60 mL/min) q12h from Day 1 through Day 15.

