### 9.5. Sample Size Determination

Up to approximately 200 participants will be enrolled in this study.

The study will randomize approximately 150 participants in a 1:1:1 randomization ratio, resulting in approximately 50 participants in each treatment arm (main study population). In addition, the study will also enroll up to 50 additional nonhospitalized symptomatic participants (in a 1:1:1 randomization ratio) who are immunocompromised with a rebound in COVID-19 within 14 days following completion of an initial 5-day treatment course of nirmatrelvir/ritonavir (population with rebound).

Analyses will be conducted after the main study population is fully enrolled and have completed the Day 44 visit regardless of the number of randomized participants in the population with rebound. There will be 2 analysis time points for reporting the results of this study. The primary analysis will be performed after all participants in the main study population have completed the Day 44 visit. The follow-up analysis will be performed after all participants in the main study population have completed the Week 24 visit. In addition, both analyses (primary and follow-up) will include separate results for the main study population and the additional population with rebound.

As no formal hypothesis testing will be performed for this study, no power calculation was carried out to assess the number of participants required for each treatment arm. For the main study population, the goal of the primary analysis is to estimate the treatment effect for each duration of nirmatrelvir/ritonavir. The smaller numbers of participants in these groups will be reflected in the precision of the estimate of the primary endpoint. Table 2 displays which effect sizes would be excluded based on the expected width of the confidence interval around the estimate of the proportion of participants with sustained NP swab SARS-CoV-2 RNA <LLOQ (defined as <2.0 log10 copies/mL) from Day 15 through Day 44 with a sample size of 50.

When the proportion of participants with sustained NP swab SARS-CoV-2 RNA <LLOQ from Day 15 through Day 44 ranges from 0.1 to 0.5, Table 2 displays the precision (width of the confidence interval) for the respective proportion to be estimated with a sample size of 50. That is, the width of the 95% CI does not exceed 14%.

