5. GENERAL METHODOLOGY AND CONVENTIONS

5.1. Hypotheses and Decision Rules

No formal hypothesis testing will be performed for this study.

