6.1.1. Main Analysis

The primary descriptive analysis will summarize, separately for the main study population and the population with rebound, the number and proportion of participants with sustained NP swab SARS-CoV-2 RNA <LLOQ (defined as <2.0 log₁₀ copies/mL) from Day 15 through Day 44 for each treatment arm in the Evaluable Analysis Set and FAS. Participants DMB02-GSOP-RF02 7.0 *Statistical Analysis Plan Template* 31-Jan-2022

> PFIZER CONFIDENTIAL TMF Doc ID: 98.03 Page 16 of 32

receiving non-study antiviral or monoclonal antibody therapy post-baseline (between randomization and Day 44 visit) for the treatment of COVID-19 will be considered as not achieving sustained NP swab SARS-CoV-2 RNA <LLOQ in the primary analysis.

As viral load measurements from NP swabs are taken on Days 15, 21, 28, 35, and 44 during the time interval from Day 15 to Day 44, all of the measurements that are non-missing must be <LLOQ (including undetectable), and the Day 15, Day 44, and no more than one of the Day 21, 28, and 35 measurements can be missing in order for the event to be considered sustained.

In addition, 95% CIs for the proportion of participants with sustained NP swab SARS-CoV-2 RNA <LLOQ from Day 15 through Day 44 for each treatment arm will be calculated using binomial distribution normal approximation. The difference in proportions for the primary endpoint and associated 95% CI will be calculated for each pairwise comparison of the treatment arms.

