The Day 35 visit is the last possible day the sustained NP swab SARS-CoV-2 RNA<LLOQ can be achieved.

DMB02-GSOP-RF02 7.0 Statistical Analysis Plan Template 31-Jan-2022 PFIZER CONFIDENTIAL TMF Doc ID: 98.03 Page 18 of 32 The time to the sustained event is defined as:

- For a participant with sustained event at Day *t*, the First Event Date is the date of the Day *t* measurement, and time to event will be calculated as (First Event Date) (First Dose Date) +1.
- For a participant for which no possible value of *t* ≤ the 35 visit satisfies the criteria for a sustained event (censored), censoring date will be the date of the last available protocol-specified SARS-CoV-2 RNA measurement other than Day 44, and time will be calculated as (Censoring Date) (First Dose Date) +1.

Time to sustained NP swab SARS-CoV-2 RNA<LLOQ will be summarized graphically using Kaplan-Meier plots for each of the treatment groups in main study population.

6.2.3. Proportion of participants with SARS-CoV-2 RNA <LLOQ in plasma over time.

• The proportion of participants with SARS-CoV-2 RNA <LLOQ as measured in plasma will be summarized at each study visit through week 24 for each treatment arm. In addition, 95% CIs for the proportion of participants with SARS-CoV-2 RNA <LLOQ in plasma at each study visit will be calculated for each treatment arm.

6.2.4. Proportion of participants with SARS-CoV-2 RNA level in NP swabs <2.0 log₁₀ copies/mL at each study visit

The proportion of participants with SARS-CoV-2 RNA < 2.0 log₁₀ copies/mL as measured by NP swab will be summarized at each study visit through Week 24 for each treatment arm. In addition, 95% CIs for the proportion of participants with SARS-CoV-2 RNA <2.0 log₁₀ copies/mL as measured by NP swabs at each study visit will be calculated for each treatment arm.

6.2.5. Change from baseline in SARSCoV-2 RNA level in NP swabs and in plasma over time.

Descriptive statistics by treatment group for the change from baseline to each study visit (Day 5, 10, 15, 21, 28, 35, 44) will be provided. Participants are excluded from the analysis for reasons of Not Detected, Zero or Missing baseline and/or post-baseline viral load results.

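### The primary endpoint carries two non-equivalent rules for a sustained result, and neither document says which one governs

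*SAP*

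**What the plan says.** The endpoint is named in Protocol 9.3.2.1 and SAP 3.1 and 6.1 as the proportion with sustained RNA below LLOQ (below 2.0 log10 copies/mL) from Day 15 through Day 44. The next sentence in each place defines sustained as no value of 2.0 log10 or more "at any study visit (through Day 44) following the first study visit where the" participant's swab is below LLOQ. That sentence has an end (Day 44) but its start is each participant's first clear visit, whenever it falls.

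SAP 6.1.1 gives a different test. It lists the swabs of Days 15, 21, 28, 35 and 44 and says that "all of the measurements that are non-missing must be <LLOQ (including undetectable". It then adds that "the Day 15, Day 44, and no more than one of the Day 21, 28, and 35 measurements can be missing" for the event to count. Days 5 and 10 are not mentioned.

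RNA is measured before Day 15: SAP 6.2.5 summarises change from baseline to "each study visit (Day 5, 10, 15, 21, 28, 35, 44". The 5-day arm takes active drug "q12h from Day 1 through Day 5 followed by placebo"; the 10-day arm takes it "q12h from Day 1 through Day 10 followed by placebo" (Protocol 1.1, Study Arms and Duration). SAP 2.1 reports modifications to the protocol's analysis plan as not applicable.

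**The concern.** Two programmers working from the same SAP could derive different primary outcomes for the same participant. One would follow the first-clear-visit sentence and read the Day 5 and Day 10 swabs; the other would follow 6.1.1 and ignore them. The protocol contains only the first rule, so if 6.1.1 is the operative one, an undeclared change of definition sits in the SAP. Protocol Section 9 says that major modifications of the primary endpoint definition will also be reflected in a protocol amendment.

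The effect need not be equal across arms. Duration of active drug is the randomised factor, and the two rules part company over swabs taken while some arms are on drug and another is not. The pairwise differences in proportions are planned outputs (SAP 6.1.1). None of the five supplementary analyses in SAP 6.1.2 applies the other rule, so the report would not show how much depended on the choice.

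**Working it through.** **Inputs.** Post-baseline RNA visits through Day 44: Days 5, 10, 15, 21, 28, 35 and 44 (SAP 6.2.5). Sample size: randomisation 1:1:1, "resulting in approximately 50 participants in each treatment arm (main study population" (Protocol 9.5). Interval method: normal approximation to the binomial (SAP 6.1.1).

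**Step 1: the plan's own precision figure.** The formula 1.96 × √(p(1−p)/50) gives 0.083, 0.111, 0.127, 0.136 and 0.139 for p = 0.1, 0.2, 0.3, 0.4 and 0.5. These match Table 2, but they are half-widths, although the table labels them widths. At p = 0.5 the full width is 2 × 0.1386 = 0.277.

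**Step 2: where the rules disagree.** Take complete data, baseline at or above LLOQ, and read the first-visit sentence together with the requirement to be clear from Day 15. Success under 6.1.1 needs Days 15 to 44 all clear, which leaves four combinations at Days 5 and 10:

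| Day 5 | Day 10 | Days 15–44 | SAP 6.1.1 | First-visit rule |
|---|---|---|---|---|
| ≥LLOQ | ≥LLOQ | all <LLOQ | success | success (first clear Day 15) |
| ≥LLOQ | <LLOQ | all <LLOQ | success | success (first clear Day 10) |
| <LLOQ | <LLOQ | all <LLOQ | success | success (first clear Day 5) |
| <LLOQ | ≥LLOQ | all <LLOQ | success | **failure** |

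Exactly one pattern splits. Enumeration of every clear/not-clear sequence over the seven visits gives the same result.

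**Step 3: baseline.** SAP 6.1.2 item 3 removes participants below LLOQ at baseline in a supplementary analysis, so they are in the primary one. If baseline counts as a study visit, those who are then at or above LLOQ at Day 5, Day 10 or both, and clear from Day 15 on, also pass 6.1.1 and fail the first-visit rule. Of these, the participant who is clear at Day 5 and not clear at Day 10 splits even if baseline does not count.

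**Step 4: which arm.** At the nominal Day 10 visit the 5-day arm is off active drug and the other two arms are not. The first nominal off-drug visit in the 10-day arm is Day 15, which both rules read. Exclusivity does not follow. Values can fluctuate around LLOQ on treatment in any arm. The SAP's reporting window for Day 10 also runs to Day 12 (Appendix 2.1), so some 10-day participants can be swabbed off drug.

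**Step 5: size.** One participant is 1/50 = 2 points on an arm and on each difference involving it. The share of the 5-day arm showing the split pattern is not given anywhere. For assumed shares:

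| Assumed share | Participants of 50 | Shift |
|---|---|---|
| 0.8% | 0.4 | 0.8 points |
| 2% | 1 | 2 points |
| 5% | 2.5 | 5 points |
| 10% | 5 | 10 points |

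The 0.8% is borrowed from the only rebound rate in the documents (4/483, Protocol 2.2). That figure is symptom rebound in high-risk patients, not this RNA pattern, and serves only as a low anchor.

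**Step 6: comparator.** The quantity affected is a difference, with half-width 1.96 × √(2p(1−p)/50). This is 0.196 at p = 0.5 and 0.180 at p = 0.7. As an illustration, suppose both arms are 25/50 under 6.1.1: difference 0.00 (−0.196 to 0.196). If 5 participants in the 5-day arm are reclassified under the first-visit rule, it becomes 20/50 against 25/50: difference 0.10 (−0.094 to 0.294).

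**Step 7: the same sentence in SAP 6.2.2.** Time to sustained clearance repeats the first-visit sentence, then takes the earliest visit meeting criteria a to d. For the split pattern, Day 15 meets all four, so the criteria give an event at Day 15. The sentence above them says the result was not sustained.

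**The case against.** The best defence is that the governing rule is not really open. SAP 6.1.1 is the main-analysis section, names the five swabs, and states what is needed for the event to count. It also fits the recorded reason for the Day 15 start, a standard follow-up period for all arms (Protocol, Amendment 1 summary). If the phrase fixing the endpoint from Day 15 also bounds the definition that follows it, results before Day 15 count under neither text and the conflict disappears. In addition, "No formal hypothesis testing will be performed for this study", so no decision flips. Early off-drug rebound is also reported elsewhere: SAP 6.2.6 counts it from the end of active treatment, and SAP 6.2.4 gives the proportion clear at each visit.

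Much of this stands. The calendar rule is probably the one intended and the likelier one to be programmed. But the documents do not say so, the protocol contains only the other sentence, and on this defence that sentence adds nothing and can be replaced.

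A reader might infer more than the documents support:

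- **Late clearers.** Someone first clear at Day 28 looks sustained if the definition is read alone. The sentence before it requires clearance from Day 15, so this participant fails under both texts.
- **All early rebounders.** A 5-day participant who rebounds and is still at or above LLOQ at Day 15 fails both rules. Only those clear again at Day 15 and through Day 44 change class.
- **The 5-day arm only.** Step 4 shows why this is a tendency and not a certainty.
- **A known, large shift.** No document gives a rate for the pattern, so no particular size can be claimed.

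**Conclusion.** The primary endpoint has two rules that are not equivalent and no order of precedence. With baseline at or above LLOQ and complete data, they disagree on one pattern: clear at Day 5, not clear at Day 10, clear from Day 15 through Day 44. Some participants below LLOQ at baseline are added if baseline counts as a visit. The choice can shift arm differences, most plausibly through the 5-day arm, by 2 points per reclassified participant. Over an assumed share of 0.8% to 10% of that arm the shift is 0.8 to 10 points, against a half-width of about 18 to 20 points (assuming 50 per arm and true proportions of 0.7 to 0.5). The size is therefore unproven and may be small. The reason to act is that a primary outcome should have one derivation, and that a rule reading swabs before Day 15 works against the common follow-up period the Day 15 start was meant to provide.

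**What to change.** 1. In Protocol 9.3.2.1 and SAP 3.1 and 6.1, replace the first-clear-visit sentence with the calendar rule of SAP 6.1.1: all available scheduled nasopharyngeal swabs from the Day 15 visit through the Day 44 visit are below 2.0 log10 copies/mL, and baseline, Day 5 and Day 10 results are not considered.
2. Reword the missing-visit sentence in SAP 6.1.1. As written it says that Day 15 and Day 44 can be missing; it should state plainly whether those two swabs are required. It should not be carried into the new definition unchanged.
3. In SAP 6.2.2, align the opening definition with criteria a to d, which allow rebound followed by renewed clearance. Keeping the first-visit sentence there would leave the same mismatch in place.
4. Tabulate, by arm, the participants whose class changes under the first-visit rule.
5. Record the clarification in SAP 2.1 if the SAP is changed before the protocol.

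The cost is a few sentences in the SAP, a matching protocol edit (handled as an amendment if the sponsor judges it major under Protocol Section 9), and one extra table. No new data are needed.

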6.1.1. Main Analysis

The primary descriptive analysis will summarize, separately for the main study population and the population with rebound, the number and proportion of participants with sustained NP swab SARS-CoV-2 RNA <LLOQ (defined as <2.0 log₁₀ copies/mL) from Day 15 through Day 44 for each treatment arm in the Evaluable Analysis Set and FAS. Participants DMB02-GSOP-RF02 7.0 *Statistical Analysis Plan Template* 31-Jan-2022

> PFIZER CONFIDENTIAL TMF Doc ID: 98.03 Page 16 of 32

receiving non-study antiviral or monoclonal antibody therapy post-baseline (between randomization and Day 44 visit) for the treatment of COVID-19 will be considered as not achieving sustained NP swab SARS-CoV-2 RNA <LLOQ in the primary analysis.

As viral load measurements from NP swabs are taken on Days 15, 21, 28, 35, and 44 during the time interval from Day 15 to Day 44, all of the measurements that are non-missing must be <LLOQ (including undetectable), and the Day 15, Day 44, and no more than one of the Day 21, 28, and 35 measurements can be missing in order for the event to be considered sustained.

In addition, 95% CIs for the proportion of participants with sustained NP swab SARS-CoV-2 RNA <LLOQ from Day 15 through Day 44 for each treatment arm will be calculated using binomial distribution normal approximation. The difference in proportions for the primary endpoint and associated 95% CI will be calculated for each pairwise comparison of the treatment arms.

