2.2.1. Primary Estimand(s)

The primary estimand, reported separately for the main study population and the population with rebound, is the proportion of participants with sustained NP swab SARS-CoV-2 RNA <LLOQ (defined as <2.0 log₁₀ copies/mL) from Day 15 through Day 44 in nonhospitalized symptomatic patients \geq 12 years of age with COVID-19 who are immunocompromised. This will be estimated without regard to study treatment discontinuation and considering participants receiving non-study antiviral or monoclonal antibody therapy post-baseline for the treatment of COVID-19 as not achieving sustained NP swab SARS-CoV-2 RNA <LLOQ.

DMB02-GSOP-RF02 7.0 Statistical Analysis Plan Template 31-Jan-2022 PFIZER CONFIDENTIAL TMF Doc ID: 98.03 Page 9 of 32

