6.2.1.1. Main Analysis

Time (days) to first NP swab SARS-CoV-2 RNA<LLOQ (<2.0 log₁₀ copies/mL) will be evaluated for participants with NP swab SARS-CoV-2 RNA \geq LLOQ at baseline. The first day of NP swab SARS-CoV-2 RNA<LLOQ will be considered the First Event Date. Time

DMB02-GSOP-RF02 7.0 Statistical Analysis Plan Template 31-Jan-2022 PFIZER CONFIDENTIAL TMF Doc ID: 98.03 Page 17 of 32 (days) to first NP swab SARS-CoV-2 RNA<LLOQ will be calculated as (First Event Date) – (First Dose Date) +1.

There are limitations to the timing of the first event date as NP viral RNA is generally only captured at in-person scheduled visits during the study.

The Day 44 visit day is the last possible day the NP swab SARS-CoV-2 RNA<LLOQ can be achieved.

For a participant that either completes the Day 44 visit of the study or discontinues from the study before the Day 44 visit without NP swab SARS-CoV-2 RNA<LLOQ (censored), censoring date will be at the last date on which NP swab SARS-CoV-2 RNA is assessed, and time will be calculated as (Censoring Date) – (First Dose Date) +1 or the Day 44 visit whichever occurs first.

Time to NP swab SARS-CoV-2 RNA<LLOQ will be summarized graphically using Kaplan-Meier plots for each of the treatment groups in main study population.

6.2.2. Time to sustained NP swab SARS-CoV-2 RNA <LLOQ (<2.0 log10 copies/mL) through Day 44 for participants with NP swab SARS-CoV-2 RNA ≥LLOQ at baseline

Time (days) to sustained NP swab SARS-CoV-2 RNA<LLOQ (<2.0 log₁₀ copies/mL) will be evaluated. Sustained is defined as NP swab SARS-CoV-2 RNA level not \geq 2.0 log₁₀ copies/mL at any study visit (through Day 44) following the first study visit where the participant's NP swab SARS-CoV-2 RNA <LLOQ.

Let *t* represent the number of days between 5 and 35 inclusive for which there is a protocol-specified measurement of SARS-CoV-2 RNA level on Day *t*.

Then a sustained event will correspond to the first possible value of *t* to satisfy the following criteria:

- a) The Day 44 SARS-CoV-2 RNA level is <LLOQ
- b) The Day t SARS-CoV-2 RNA level is <LLOQ
- c) All available (non-missing) protocol-specified SARS-CoV-2 RNA measurements between Day *t* and Day 44 are <LLOQ
- d) No more than one of the protocol-specified SARS-CoV-2 RNA measurements between Day *t* and Day 44 are missing.

There are limitations to the timing of the first event date as NP viral RNA is generally only captured at in-person scheduled visits during the study.

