8. APPENDICES

Endpoint	Analysis Type	Population	Data Inclusion and Rules for Handling Intercurrent Events and Missing Data	Analysis Model
Proportion with sustained SARS- CoV-2 RNA < LLOQ from Day 15 to Day 44 (NP)	Primary	Evaluable, FAS	Intercurrent event: non-study anti- viral or mAb therapy – participant considered failure No imputation of missing data	Descriptive (n, %), 95% CI for proportion and the difference in proportion using binomial distribution normal approximation
Proportion with sustained SARS- CoV-2 RNA < LLOQ from Day 15 to Day 44 (NP)	Supplementary	Evaluable	Intercurrent event: non-study anti- viral or mAb therapy – data excluded/considered missing No imputation of missing data	Descriptive (n, %), 95% CI for proportion and the difference in proportion using binomial distribution normal approximation
Proportion with sustained SARS- CoV-2 RNA < LLOQ from Day 15 to Day 44 (NP)	Supplementary	Evaluable	Intercurrent event: non-study anti- viral or mAb therapy – data included as is No imputation of missing data	Descriptive (n, %),95% CI for proportion and the difference in proportion using binomial distribution normal approximation
Proportion with sustained SARS- CoV-2 RNA < LLOQ from Day 15 to Day 44 (NP)	Supplementary	Evaluable	Participants with baseline SARS- CoV-2 RNA level <lloq be
excluded Intercurrent event: non-study anti- viral or mAb therapy – participant considered failure</lloq>	Descriptive (n, %), 95% CI for proportion and the difference in proportion using binomial distribution

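### SAP 6.1.1, as worded, lets the Day 15 and Day 44 swabs be missing in a participant counted as sustained from Day 15 through Day 44, and the denominator for incomplete participants is left unreconciled with SAP 5.3

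*SAP*

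**What the plan says.** - **Endpoint.** SAP 3.1 and 6.1 and Protocol 9.3.2.1 define the primary endpoint as the proportion with sustained NP swab RNA below LLOQ from Day 15 through Day 44.
- **Completeness rule.** SAP 6.1.1 lists swabs on Days 15, 21, 28, 35 and 44. Every non-missing result must be below LLOQ, and "the Day 15, Day 44, and no more than one of the Day 21, 28, and 35 measurements can be missing" for the event to count as sustained.
- **Related endpoint.** SAP 6.2.2 (time to sustained clearance, participants at or above LLOQ at baseline) sets as criterion (a) "The Day 44 SARS-CoV-2 RNA level is <LLOQ" and as criterion (b) "The Day t SARS-CoV-2 RNA level is <LLOQ". Criterion (d) adds: "No more than one of the protocol-specified SARS-CoV-2 RNA measurements between Day" *t* and Day 44 may be missing.
- **Missing data in general.** SAP 5.3 rules out imputing missing RNA data and says that "missing endpoint data will result in a summary where the N for that endpoint (and time point) is smaller than the total N" of the analysis set.
- **Appendix 1.** The primary row, on non-study therapy and missing data, reads "participant considered failure No imputation of missing data". The rows for the by-visit NP and plasma proportions instead count a missing timepoint as not below LLOQ.
- **Estimand.** SAP 2.2.1: "This will be estimated without regard to study treatment discontinuation and considering participants receiving non-study antiviral or monoclonal antibody therapy" as failures. It does not mention death, withdrawal or missed swabs.

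**The concern.** The endpoint claims clearance up to Day 44. The rule that produces it, followed as written, credits that claim to participants with no Day 44 result, and even to participants with neither a Day 15 nor a Day 44 result. Someone who withdraws or dies after the Day 28 or Day 35 swab can be a responder. If at or above LLOQ at baseline, the same person is censored without an event in SAP 6.2.2.

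A second gap concerns the denominator. SAP 6.1.1 makes completeness a condition of being sustained, which suggests that an incomplete participant is a non-responder who stays in N. SAP 5.3 says missing endpoint data reduce N, but not when a five-visit composite is missing. Two programmers could report different primary proportions from the same data. The trial has no hypothesis test, so these proportions and their pairwise differences are its primary result.

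**Working it through.** **Inputs.** The five swab days and the completeness sentence come from SAP 6.1.1, the criteria for the related endpoint from SAP 6.2.2, and about 50 participants per arm from SAP 2.4. The documents give no missing-swab or dropout rate.

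**The plan's precision figure.** The normal-approximation half-width at p = 0.5 and n = 50 is 1.96 × √(0.5 × 0.5 / 50) = 0.1386. This reproduces the 0.139 in Table 2, which is a half-width although labelled a width (a separate matter).

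**Patterns.** Take a participant negative at every observed swab. Five visits give 2⁵ = 32 missing-swab patterns.

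- As written, Day 15 is free (2 options), Day 44 is free (2), and at most one of Days 21, 28 and 35 is missing (1 + 3 = 4). That gives 2 × 2 × 4 = **16** passing patterns, with a minimum of 3 − 1 = 2 observed swabs.
- If Days 15 and 44 are required: 1 × 1 × 4 = **4** patterns, with a minimum of 4 observed swabs.
- Among the 16, Day 44 is missing in 2 × 4 = **8**, and Days 15 and 44 are both missing in 4.

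**Dropout.** Suppose all swabs are present until dropout. With a last swab on Day 35, only Day 44 is missing and the participant passes. With a last swab on Day 28, Days 35 and 44 are missing, which is one middle visit, and the participant passes. With a last swab on Day 21, two middle visits are missing and the participant fails. The reporting windows in SAP Appendix 2.1 do not rescue this: a missing Day 44 value means no swab on Days 40 to 49.

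**Against SAP 6.2.2.** All 8 patterns with Day 44 missing fail criterion (a) at every *t*, so no sustained event is possible. The 4 patterns missing Day 15 but not Day 44 fail only at *t* = 15. With Day 21 observed, *t* = 21 qualifies; with Day 21 missing, *t* = 28 does.

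**Size.** Suppose k of 50 in an arm are negative through a last swab on Day 28 or 35, in a passing pattern, with none later. The rule as written counts all k. The unobserved true number is 0 to k, so the overstatement is 0 to k/50, that is 0 to 2k percentage points. Assumed example: 25 of 50 fully observed and sustained, k = 3.

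- As written: 28/50 = 56.0%
- Days 15 and 44 required, incomplete kept in N as not sustained: 25/50 = 50.0%
- Days 15 and 44 required, incomplete removed from N: 25/47 = 53.2%

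The first and second differ by 6.0 points. The denominator choice alone accounts for 3.2.

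**The case against.** **It is a slip that any programmer would read correctly.** Very likely it is a slip: words requiring Days 15 and 44 seem to have dropped out, and SAP 6.2.2 shows the intent. But 6.2.2 governs a different endpoint in a baseline subset, and the primary rule stands uncorrected.

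**The denominator is already covered.** A reader might infer that the SAP is silent on it. It is not: SAP 5.3 gives a general rule, and the Appendix 1 primary row rules out imputation. Where the SAP wants missing counted as failure, as in the by-visit rows, it says so, which favours removal from N. What remains is narrower: nothing says whether failing the 6.1.1 condition is missing endpoint data or simply not sustained. Counting incomplete participants as non-responders is thus a preference, not something the documents dictate.

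**The clash with SAP 6.2.2 can be overstated.** Twelve of the 16 patterns fail 6.2.2 at *t* = 15, but four of them can still have an event at another *t*. The firm conflict is the 8 with Day 44 missing. Pattern counts are also not frequencies.

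**The effect is modest.** The assumed 6 points sit well inside a half-width of 13.9. A reader might also infer that unequal dropout would reverse an arm comparison. Assumed extremes can do that: with 10 affected in one arm and 2 in another, and half of the rest sustained, the difference is 30/50 − 26/50 = +8 points as written and 20/50 − 24/50 = −8 with incomplete participants kept as not sustained. But no document gives such rates, and with no hypothesis test or decision rule, no planned conclusion is shown to change. This limits the size of the point. It does not make the sentence right.

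**Conclusion.** The point holds in two parts and should be settled before the primary proportion is programmed.

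First, the SAP 6.1.1 sentence is wrong as written. It admits 16 missing-swab patterns where requiring Days 15 and 44 admits 4, and in 8 of the 16 it declares clearance through Day 44 without a Day 44 result. This rests on the text alone.

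Second, SAP 5.3 and 6.1.1 are not reconciled for participants who fail completeness. That is a missing link between two rules, not the absence of a rule.

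The numerical effect can only be bounded: 0 to 2k points for k affected participants in an arm of 50. The 6-point figure rests on an assumed k = 3 and is an upper limit for that case. The documents do not support saying that the primary result will be inflated by any particular amount.

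**What to change.** 1. In SAP 6.1.1, replace the completeness sentence with: *Day 15 and Day 44 must both be non-missing, no more than one of Days 21, 28 and 35 may be missing, and all non-missing results must be <LLOQ.*
2. In SAP 6.1.1 and the Appendix 1 primary row, state whether a participant who fails completeness is not sustained and kept in N, or missing under SAP 5.3 and removed from N. The choice is the sponsor's. Keeping them in N gives the lower proportion and departs from 5.3; removing them fits the no-imputation wording of the primary row but differs from how Appendix 1 treats the by-visit proportions.
3. Report the other version as a sensitivity analysis, with completeness failures tabulated by arm.
4. Optional and editorial: align the sentence that defines sustained from the first negative study visit (SAP 3.1, 6.1; Protocol 9.3.2.1) with the Day 15 to Day 44 rule. A participant negative on Day 5, positive on Day 10 and negative from Day 15 on passes SAP 6.1.1 but fails that sentence.

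The cost is SAP wording and one extra sensitivity table, with no new data. Protocol 9.3 leaves missing-data procedures to the SAP. A protocol amendment is needed only if the sponsor regards the change as a major modification under Protocol Section 9.
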